6 prerequisite for receiving the TeGeCoach intervention; participants can elect their preferred physician
7 prior to program start, or are alternatively referred to an already contracted physician by their health
8 coach. To encourage physicians to participate, they enter into an integrated care contract with the
9 respective health insurance fund that provides financial incentives for the delivery of special medical
10 services throughout the intervention.⁶⁷ The enrolment and reimbursement of contracted physicians is
11 coordinated by medicalnetworks (Kassel, Germany), a company that is specialized on the management
12 of integrated care programs (ICPs) within the § 140a volume V of the German Social Security Code (SGB
13 V). If the physician of choice refuses to participate, the participant is referred to a nearby contracted
14 physician that has already entered into the integrated care contract. Once enrolled, the health coach
15 contacts the contracted physician to discuss their tasks during the course of the study. Due to
16 recruitment barriers, it is possible that no suitable physician can be found for the patient by the end of
17 the recruitment phase. For safety reasons, participants for whom no physician can be appointed do not
18 receive TeGeCoach.

19

20 **Treatment allocation and blinding**

21 Participants are allocated in a 1:1 ratio to either the TeGeCoach or CAU group, stratified by health
22 coaching center using a permuted block method within each stratum. In order to prevent selection bias
23 and to eliminate any predictability (allocation concealment), participants are randomly allocated via
24 Sealed Envelope (London, United Kingdom), a secure internet-based randomization service including
25 concealment, stratification and blocking for each health coaching site.

26 Blinding of care providers (health coaches and contracted physicians) and participants is not possible
27 because of obvious differences between the TeGeCoach intervention and CAU. However, as supported
28 by the CONSORT guidelines, blinding of the analysis is achieved by engaging an independent data analyst
29 and by withholding information about how the groups were coded before analytical decisions have been
30 completed.⁶⁸

31

32 **Interventions**

33 *TeGeCoach*

34 TeGeCoach is a 12-month long structured HEP that is designed to inspire healthy habits in patients
35 with PAD based on the transtheoretical model of behavior change. The main strategies used to improve

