14 Center of *mhplus Krankenkasse*), and are staffed with licensed health workers (e.g. nurses, physical
15 therapists, medical assistants, etc.). To ensure high-quality health coaching, health coaches are regularly
16 supervised by a team of experts and receive 51 hours of training, including 19 hours of program training,
17 seven hours of medical training, eight hours of group supervision and one hour of individual supervision.
18 Compliance to coaching guidelines are continuously monitored and reviewed. In addition to the
19 structured TeGeCoach intervention, participants have regular access to usual care (CAU) as described
20 below.

21 After 12 months, there is an additional 12 months of unstructured follow-up in which patients
22 have no interaction with their health coach but still have access to their activity tracker device, which
23 they may continue to use to self-monitor their physical activity.

24

25 *Care as usual (CAU)*

26 Patients allocated to CAU receive usual medical care through the regular statutory health care
27 system. Additionally, participants receive PAD patient information leaflets from their statutory health
28 insurance fund, with each health insurance fund providing its own leaflets. These leaflets provide
29 information about course offerings of the respective health insurance fund to encourage regular
30 exercise and to promote lifestyle changes, including SEPs (vascular and cardio exercise), physical
31 therapy, nutritional assistance programs, smoking cessation programs, weight loss programs, as well as
32 patient education programs for obesity and diabetes. It is thereby ensured that participants allocated to
33 CAU receive genuine usual care as supplied in everyday practice.

34

35 **Outcome Measures**

1 Outcome measures are listed in Table 2 along with timing of assessment; the effectiveness of
 2 TeGeCoach is measured based upon PROMs, claims data, activity tracker data. PROMs are collected at
 3 baseline (t0), at 12 (t1) and 24 (t2) months.

4

5 *Primary Outcomes*

- 6 - *PROM: Walking impairment (Walking Impairment Questionnaire, WIQ)* ⁶⁹⁻⁷²

7

8 *Secondary Outcomes*

- 9 - *PROMs: Generic health-related quality of life (EQ5D-5L & SF-12 questionnaires)* ⁷³⁻⁷⁶ ; PAD-
 10 specific quality of life (VascuQoL-25 questionnaire) ^{77 78}; depression (PHQ-9 questionnaire) ⁷⁹;
 11 generalized anxiety disorder (GAD-7 questionnaire) ^{80 81}; alcohol use (AUDIT-C questionnaire)

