10 for small changes on the WIQ following three months of a structured HEP that have been determined in

11 previous studies (WIQ speed MCID: 6%; WIQ distance MCID: 5%; WIQ stair climbing MCID: 5%).⁹¹ As

12 TeGeCoach is more intensive and longer, a small-to-moderate group difference was estimated (f=0.15),

13 while accounting for the inherited heterogeneity of this pragmatic trial that could lead to a dilution of

14 the treatment effect. Assuming a response rate of 30% (TeGeCoach) and 20% (CAU) from baseline 24-

15 month follow-up (t2)^{43 92}, a sample size of 1760 (880 per group) is required to have 176 and 264

16 participants at t2 in the CAU and intervention arm, respectively, which is sufficient to detect the

17 estimated small-to-moderate effect with 80% power and a 5% level of significance (Gpower v.3.1.9.2).

18

19 **Data collection and management**

20 Data management and storage are carried out in compliance with the General Data Protection

21 Regulation (GDPR) in the European Union and Good Scientific Practice guidelines by the German

22 Research Foundation.⁹³ To ensure confidentiality, all data are collected, processed, analyzed and stored

23 in de-identified form by replacing personally identifying information of each participant with a unique

24 patient identification number (i.e. by pseudonymization), which allows to combine data from multiple

25 sources and to merge longitudinal data. Linkage to an identity (depseudonymization) is not possible

26 without a separately stored pseudonymization key, which is protected by technical and organizational

27 measures.

28 At each study point, the data coordinators of the health insurance funds send out a set of paper-

29 based questionnaires (PROMs) to the participants. Participants are asked to send them back to the

30 Department of Medical Psychology at the University Medical Center Hamburg-Eppendorf. To maximize

31 response rates, participants who have not send their questionnaire back in time receive a postal

32 reminder after 2-4 weeks. All participants are followed up at t1 and t2, irrespective of whether

33 questionnaires have been returned at previous study points. Questionnaire data are entered into an

1 electronic database, with only authorized personnel being allowed to retrieve, enter or change data. For
2 data quality and monitoring purposes, validation checks regarding out of range data, illogical and invalid
3 responses and data entry errors are performed.

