4 Claims data are routinely collected for the purpose of billing and contains information on all contacts
5 with the health care system including ICD codes, operations and procedure key (OPS) codes (the German
6 equivalent to the American procedure coding system, PCS), medication prescriptions and amount of sick
7 leaves. After study completion, the health insurance funds assemble and pseudonymize the claims data
8 and send it to the study team (University Medical Center Hamburg-Eppendorf). No individual insurance
9 information can be identified from this data.

10 Activity tracker data are automatically uploaded to the electronic documentation system via SIM card
11 modem (econnect, IEM GmbH) once per day. The statutory health insurance funds share the activity
12 tracker data with the study team in pseudonymized form.

13 All data are stored for a maximum of 10 years, securely locked in cabinets and saved on password-
14 protected computers in areas with restricted access. Personally identifiable information of participants
15 and pseudonymization keys are only accessible to the data coordinators at each health insurance fund.
16 The pseudonymization keys are deleted two years after study completion so that virtually from this point
17 all data is fully anonymized. Regarding dissemination, all publicly available data are fully anonymized
18 and do not disclose identities. Participants have the right to be informed about their data. If a participant
19 decides to withdraw from the trial prematurely, the data already collected may be used, unless revoking
20 their informed consent. Deletion of the data cannot be requested if the data has already been
21 anonymized.

22

23 **Statistical analysis**

24 Analyses are by intention-to-treat in accordance with the CONSORT guidelines, i.e. participants who
25 do not adhere to or withdraw from the prescribed TeGeCoach intervention and for whom no doctor
26 could be appointed (see *recruitment* section) are included in the analyses as randomized. For
27 questionnaire data, changes from baseline to follow-up measurements are compared between study
28 arms using linear mixed models.⁹⁴ Single imputation using the Expected-Maximization algorithm are
29 applied for item-level missing data. Scale-level imputation of missing data is not necessary since this is
30 fully handled by estimating mixed models with full information maximum likelihood (FIML).^{95 96} In order

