31 to take correlation between the observations into account, models are adjusted for participant and
32 health coaching center characteristics. For claims data, changes over time between groups are
33 compared between study arms using random-effects regression models (difference-in-differences
34 method) after eliminating differences in observable baseline characteristics between groups with the
35 use of entropy balancing⁹⁷. Entropy balancing allows a better balancing compared to conventional

1 processes such as propensity matching. Tests of treatment effects are conducted at a two-sided
2 significance level of 0.05. In order to check the robustness of the results, subgroup analyses are
3 performed to determine the influence of baseline characteristics (e.g. degree of walking impairment),
4 health insurance fund (i.e. *KKH Kaufmännische Krankenkasse*, *TK Techniker Krankenkasse*, *mhplus*
5 *Krankenkasse*) and type of analysis (i.e. intention-to-treat and per-protocol).

6

7 **Data monitoring and harms**

8 This trial is not monitored by a data monitoring committee, and no interim analyses are performed
9 as TeGeCoach is a low risk, non-invasive intervention with no identifiable risks. Over the course of the
10 intervention, participants allocated to TeGeCoach are medically monitored by their treating physician
11 while having regular access to the usual care of PAD. The risks from the use of wearable activity trackers
12 is low; all devices have been certified and conform to health, safety, and environmental protection
13 standards for products sold within the European Union (CE certificate).

14

15 **Ethics and Dissemination**

16 The study protocol, the informed consent forms and all other documents that are handed out to the
17 participants have been reviewed and approved by the ethical review bodies (Medical Association
18 Hamburg; reference number: PV5708). The ethics committee will be informed in case of any
19 amendments made to the study protocol or informed consent forms.

20 Findings are disseminated widely through peer-reviewed manuscripts published in scientific journals,
21 reports to the funding body, international conference presentations and media press releases.
22 Furthermore, the study team realizes the value of open science and feels committed to information
23 exchange through data being accessible to the research community. Therefore, in an attempt to tackle

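### The primary WIQ model commits to neither baseline adjustment nor the randomisation centre; specifying both costs nothing and gains about 1 to 2 points of power on the likelier reading, 3 to 9 on the other

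*Combined protocol and SAP*

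**What the plan says.** The Statistical analysis section states that for "questionnaire data, changes from baseline to follow-up measurements are compared between study" arms, linear mixed models are used. Missing scale scores are left to full-information maximum likelihood (FIML) within those models. On adjustment it says only that, in order "to take correlation between the observations into account, models are adjusted for participant and" health coaching center characteristics. Those characteristics are not listed. Degree of walking impairment at baseline appears later in the section, but only as an example of a subgroup factor.

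Under Treatment allocation and blinding: "Participants are allocated in a 1:1 ratio to either the TeGeCoach or CAU group, stratified by health" coaching center, with permuted blocks within each stratum. The Outcome Measures section says "PROMs are collected at" baseline, 12 and 24 months, so baseline WIQ is collected in both arms.

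The Sample size section says "a small-to-moderate group difference was estimated (f=0.15"), with 880 randomised per arm and assumed 24-month response of 30% (TeGeCoach) and 20% (usual care), giving 264 and 176. It gives no WIQ standard deviation and no correlation between baseline and follow-up.

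**The concern.** The text permits at least three models for the primary outcome: a raw change score, baseline WIQ as a covariate, or baseline WIQ as one of the repeated responses. They do not have the same precision.

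A raw change score fixes the coefficient of baseline at 1. In a randomised comparison with equal variances the efficient coefficient is rho, so the raw change is less precise for every rho below 1.

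The stated reason for adjustment is correlation between observations. That describes clustering rather than the use of a prognostic baseline score, so the sentence does not settle the matter. Nor does adjusting for characteristics of a centre commit the plan to the three-level stratum used in randomisation.

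With 70% to 80% non-response expected and different response in the two arms, the way baseline enters also decides whether a baseline difference between the two groups of responders carries into the treatment contrast.

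**Working it through.** **Inputs from the documents:** n = 264 and 176 at 24 months (880 × 0.30 and 880 × 0.20); f = 0.15, so d = 2f = 0.30; two-sided 5%.

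**Assumptions:** rho from 0.4 to 0.8; equal variances at baseline and follow-up; the 12-month data are ignored.

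**The plan's own figure.** Let b = 1/264 + 1/176 = 0.009470. The noncentrality is 0.30/√0.009470 = 3.083 on 438 df, which gives 86.8% power. The stated 80% is therefore not reproduced by a two-group test on these inputs; about 351 responders in an equal split would give 80%. An F test with 2 numerator df gives 80.8% at 440, but the plan does not state that test. The comparisons below start from 86.8%.

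**Variance of the arm difference, in outcome-SD² units:**

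- Raw change, responders only: 2(1−rho)b
- Baseline-adjusted: (1−rho²)b
- Baseline as a response, separate arm means, m baselines returned per arm: (1−rho²)b + (1−rho)²(2/m)

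The ratio of the second to the first is (1+rho)/2. At rho = 0.5 and m = 880 the three variances are 0.009470, 0.007102 and 0.007102 + 0.25 × 0.002273 = 0.007670.

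**Power with d = 0.30 in change-score SDs (noncentral t):**

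| rho | Raw change | Response, separate means, m = 880 | Baseline-adjusted | Gain over raw change | Gain over separate means |
|---|---|---|---|---|---|
| 0.4 | 86.8% | 93.8% | 95.7% | 8.9 | 1.9 |
| 0.5 | 86.8% | 92.8% | 94.4% | 7.6 | 1.7 |
| 0.6 | 86.8% | 91.6% | 93.0% | 6.3 | 1.4 |
| 0.7 | 86.8% | 90.5% | 91.6% | 4.8 | 1.1 |
| 0.8 | 86.8% | 89.3% | 90.0% | 3.2 | 0.8 |

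The separate-means column assumes that every randomised participant returns the baseline questionnaire, which the documents do not state. With fewer returned, the last term grows. For example, m = 440 (assumed) at rho = 0.5 gives 0.007102 + 0.25 × (2/440) = 0.008239, power 91.0%, and a gain of about 3.5 points instead of 1.7.

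**Power with d = 0.30 in outcome SDs, raw change against adjusted:** rho 0.4, 80.2% to 91.9% (11.7 points); 0.5, 86.8% to 94.4% (7.6); 0.6, 93.0% to 97.0% (4.0); 0.7, 97.8% to 99.1% (1.3); 0.8, 99.8% to 99.9% (0.1).

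**Baseline imbalance among responders.** Raw change shifts by (rho−1) times the imbalance. For an assumed 0.10 SD at rho = 0.5 this is −0.05 SD. A simulation with about that imbalance and a true effect of 0.30 gave 0.249 for raw change and 0.299 for FIML with baseline as a response.

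**Centre term alone.** If centre explained 5% of the variance (assumed), the noncentrality would become 3.083/√0.95 = 3.163, adding about 1.6 points.

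**The case against.** A reader might infer that the plan has chosen a raw-change analysis and so throws away about 8 points of power. The documents do not support that. The analysis is a linear mixed model with missing scale scores handled by FIML, and the Data collection and management section follows everyone at both later visits whatever was returned before. That fits baseline, 12 and 24 months as repeated responses better than a change score among responders. In such a model the arm-by-time contrast is still a comparison of changes, yet most of the lost precision is recovered. A figure of 8 points also needs rho near 0.5, which the plan does not give.

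A reader might also infer that unequal response biases the primary result by one sixth of the planned effect (0.05 out of 0.30). That shift belongs to the raw-change reading alone and rests on an assumed imbalance; with baseline as a response, FIML largely removes it.

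Nor is it right to say that centre is ignored: the adjustment sentence mentions it. The unlisted participant characteristics could include baseline WIQ, in which case a change-score model gives the same treatment estimate as adjustment for baseline. Finally, the plan's inputs give 86.8% power against a target of 80%, so the trial is not put at risk on its own assumptions.

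All of this limits the size of the point. It does not supply the missing commitment: no sentence says how baseline WIQ enters or that the stratum is a term, and both readings that leave baseline unadjusted are less precise than the alternative.

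**Conclusion.** The point holds as a free improvement in the primary model, not as a demonstrated loss of a fixed amount. On the reading that fits the text better (baseline as a response, separate arm means, all 880 baselines per arm returned), baseline adjustment or a common baseline mean gains about 2 to 1 points as rho goes from 0.4 to 0.8, and more if fewer baselines come back. On a responders-only raw-change reading it gains about 9 to 3 points if d = 0.30 is in change-score SDs, or about 12 to 0 if it is in outcome SDs. All of these figures rest on an assumed rho. The bias concern applies only to the raw-change reading. The centre term is likely to add little power, but the model should name the factor that was used to stratify.

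**What to change.** Replace the model description for questionnaire data with: *WIQ at 12 and 24 months is analysed in a linear mixed model with arm, visit, arm-by-visit, baseline WIQ, baseline-by-visit and health coaching center (three-level fixed effect).*

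Alternatively, keep baseline WIQ in the outcome vector, constrain its mean to be equal in the two arms, and include centre. This form also keeps participants who returned a follow-up but no baseline questionnaire, or the reverse, which matters with postal questionnaires and low expected response.

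Use the same form for the secondary patient-reported outcomes, each with its own baseline score. The cost is one sentence of wording. In the covariate form the model spends one baseline slope per visit and two degrees of freedom for centre. No new data and no extra participants are needed.

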25 exercise plan, checks if any contraindications to exercise exist, and whether all important comorbidities
26 such as high blood pressure, diabetes and coronary heart disease are sufficiently treated. Furthermore,
27 they receive three health reports from the health coach during the course of the program, which are
28 important for the joint exchange of information to provide collaborative care.

29 *Telephone health coaching:* Over the course of 12 months, patients regularly receive health
30 information leaflets and have up to nine structured 30-60 minute phone calls with their health coach.
31 During these structured phone calls, the health coach and the patient jointly discuss the progress
32 towards exercise goals and review the activity tracker data to check whether the patient adheres to the
33 walking plan. For this purpose, exercise sessions (i.e. intermittent walking represented as changes
34 between walking and break intervals) are visualized and automatically identified as an exercise session
35 by the health coaching platform. Additional phone calls are warranted when no data has been received,

1 no steps were taken or when coaches are alerted that the amount of exercise days has fallen below an
2 individual threshold. During these calls, barriers like lack of motivation, exercise intolerance or technical
3 issues are discussed and how they can be overcome through behavioral support. Along with the walking
4 exercise, patient-tailored topics of interest that are relevant to the management of PAD are discussed
5 in order to improve health literacy, to facilitate patient empowerment and to adopt a proactive stance
6 in dealing with their disease. The health coaching curriculum includes: Knowledge of PAD, PAD
7 medication, comorbidities of PAD and other related health topics (e.g. tobacco use, nutrition). The
8 health coaches use an electronic documentation system to monitor the coaching process (*KKH*
9 *Kaufmännische Krankenkasse* and *mhplus Krankenkasse*: Picama® Managed Care, Trustner GmbH; *TK*
10 *Techniker Krankenkasse*: Philips GmbH Market DACH). The telephone health coaching is carried out by
11 three health coaching centers that are located throughout Germany, each affiliated to one of the three
12 statutory health insurance funds (Health Coaching Center of *KKH Kaufmännische Krankenkasse*,
13 Telemedical Center at Robert-Bosch-Hospital on behalf of *TK Techniker Krankenkasse*, Health Coaching

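### Only TeGeCoach patients have a health coach, but the models carry no coach term, so standard errors can be too small and type I error can exceed 5% if outcomes vary between coaches

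*Combined protocol and SAP*

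**What the plan says.** **Who has a coach.** Under Interventions, Telephone health coaching, TeGeCoach patients "have up to nine structured 30-60 minute phone calls with their health coach". The coach reviews the walking plan and may adjust it after each session. Coaches work in three centres, one per insurance fund. The Care as usual section describes leaflets and access to ordinary services, with no coach. Patients are randomised individually 1:1, stratified by coaching centre (Treatment allocation and blinding).

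**How correlation is handled.** The Statistical analysis section specifies linear mixed models for questionnaire data. It then says that, in order "to take correlation between the observations into account, models are adjusted for participant and" centre characteristics; the sentence ends and the claims analysis begins at "health coaching center characteristics. For claims data, changes over time between groups are". Claims outcomes use random-effects regression in a difference-in-differences form, after entropy balancing. The random effects are not listed for either model. No coach term, clustered standard error, ICC or design effect appears there or under Sample size.

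**Error rate and power.** "Tests of treatment effects are conducted at a two-sided" "significance level of 0.05". Under Sample size, "a small-to-moderate group difference was estimated (f=0.15"), and the numbers are said to detect the "estimated small-to-moderate effect with 80% power and a 5% level of significance (Gpower v.3.1.9.2").

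**The concern.** Individual randomisation with clustering in one arm only is a partially nested design. Patients who share a coach may have more similar outcomes than patients who do not, because coaches differ in how they motivate patients and set plans. The TeGeCoach mean then varies more than a calculation from independent patients allows.

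The planned terms do not pick this up:

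- Fixed covariates change the mean model and leave the correlation as it was.
- A participant random effect covers repeated measures on one person.
- A centre effect is shared by both arms and largely cancels from the treatment contrast, because randomisation is stratified by centre.
- Differences between coaches inside a centre fall outside all three.

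At stake are the width of the confidence interval and the error rate of the test for the primary outcome (Walking Impairment Questionnaire) and for costs. Because the random effects are unspecified, the structure behind the primary standard error could also be settled after the data are seen.

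**Working it through.** **Step 1: the plan's own figure.** For two groups, f = 0.15 corresponds to d = 2 × 0.15 = 0.30. A two-group F test at two-sided 5% needs 176 per arm (power 80.1%; 175 per arm gives 79.9%). Then 176/0.20 = 880 per arm, 1760 in total, and 880 × 0.30 = 264. The stated sample size reproduces exactly, with independent observations and no design effect. With 264 versus 176 independent responders, power is 86.8% (86.9% by the normal approximation used below).

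**Step 2: inputs.**

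- From Sample size: 264 TeGeCoach and 176 usual-care responders at 24 months, d = 0.30.
- From Statistical analysis: two-sided 5%.
- Assumed, because the documents do not say: k = 10 to 30 coaches with equal caseloads, and coach ICC from 0 to 0.05.

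**Step 3: formulas.** With m = 264/k analysed patients per coach:

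- design effect in the TeGeCoach arm: DE = 1 + (m − 1) × ICC
- variance if clustering is ignored: V0 = 1/264 + 1/176 = 0.00947
- actual variance: V1 = DE/264 + 1/176
- actual type I error: 2 × [1 − Φ(1.96/√(V1/V0))]
- power when clustering is counted: Φ(0.30/√V1 − 1.96)

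Example with 10 coaches and ICC 0.05: m = 26.4; DE = 1 + 25.4 × 0.05 = 2.27; V1 = 2.27/264 + 1/176 = 0.01428; V1/V0 = 1.508, square root 1.228; 1.96/1.228 = 1.596; type I error 11.0%. Power is Φ(0.30/0.1195 − 1.96) = Φ(0.55) = 70.9%.

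**Step 4: results for questionnaire outcomes at 24 months.** Each cell gives type I error if the coach is ignored, then power if the coach is modelled.

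| Coaches | ICC 0 | ICC 0.01 | ICC 0.02 | ICC 0.05 |
|---|---|---|---|---|
| 10 | 5.0% / 86.9% | 6.2% / 83.6% | 7.4% / 80.2% | 11.0% / 70.9% |
| 15 | 5.0% / 86.9% | 5.8% / 84.7% | 6.6% / 82.5% | 8.9% / 76.2% |
| 20 | 5.0% / 86.9% | 5.6% / 85.3% | 6.1% / 83.7% | 7.9% / 78.9% |
| 30 | 5.0% / 86.9% | 5.4% / 85.9% | 5.7% / 84.9% | 6.8% / 81.8% |

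Across the cells with ICC above 0, the true standard error is 1.02 to 1.23 times the one that ignores coaches. The power figures use the normal approximation and make no allowance for few coaches, so they are slightly favourable.

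**Step 5: does centre adjustment repair it?** Simulation under no average effect (3000 runs per cell; model with baseline and fixed centre effects, no coach term) gave 10.9% (9 coaches), 8.7% (15) and 7.2% (30) at ICC 0.05. At ICC 0 it gave 5.0% to 5.3%. Fixed centre effects did not remove the excess.

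**Step 6: claims outcomes.** These do not depend on questionnaire return, so clusters could be larger. With 880 per arm, V1/V0 = (DE + 1)/2.

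- 30 coaches, ICC 0.005: m = 29.3, DE = 1.142, ratio 1.071, type I error 5.8%.
- 10 coaches, ICC 0.02: m = 88, DE = 2.74, ratio 1.87, type I error 15.2%.

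This puts all 880 TeGeCoach patients in coach clusters. Under Recruitment, Physicians, those for whom no physician can be appointed receive no TeGeCoach, so real clusters would be smaller. For any given number of coaches and ICC, these figures are upper bounds.

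**The case against.** **The inflation is conditional.** A reader might infer that type I error does exceed 5%. The documents do not support that: they give neither caseload nor coach ICC, and even shared coaches is an inference (a strong one, with 880 planned patients and three centres). At ICC 0 there is no excess; with many coaches and a small ICC it is tenths of a point. If TeGeCoach changes nobody's outcome, coaches create no variance and there is no inflation. The problem arises when effects differ by coach around a zero average and inference is meant to reach beyond these particular coaches. All of this stands. It does not remove the point: if the programme works to differing degrees by coach, the interval is still too narrow for that target.

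**The models are not covariate adjustment alone.** A reader might infer that the plan treats all observations as independent. It names mixed and random-effects models, and the quoted sentence may be loose wording for participant and centre effects. That stands too, but neither reading reaches the coach.

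**Planned power is not generally overstated.** Because 264 rather than 176 TeGeCoach responders are expected, there is slack. On the grid above with ICC above 0, the stated 80% is met in 9 of 12 cells and fails only at ICC 0.05 with 20 or fewer coaches.

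**The ICC may be small.** Coaches receive standard training, compliance with coaching guidelines is monitored, and contact stops at 12 months while these figures are for 24 months. This is fair for 24 months. The 12-month assessment is also listed for the primary outcome and falls as coaching ends.

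**Conclusion.** The point holds in conditional form. The design is partially nested, and the plan models correlation at participant and centre level at most. If outcomes vary between coaches within a centre, the standard error of the treatment effect is too small and the 5% test can reject too often. Under the assumed 10 to 30 coaches, type I error for the questionnaire outcomes is 5.0% at ICC 0, about 5.4% to 6.2% at ICC 0.01 and about 6.8% to 11.0% at ICC 0.05. For claims outcomes the range is 5.8% to 15.2% at ICC 0.005 to 0.02, and the top figure should be read as a ceiling for that range, not an expected value. The sample size itself reproduces and needs no criticism on this ground. This is a cheap improvement and not a defect that invalidates the trial.

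**What to change.** Replace the sentence on correlation in Statistical analysis with an explicit model for the questionnaire outcomes:

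- a within-participant covariance for the repeated measures;
- coaching centre (three levels) as a fixed effect;
- a random coach effect in the TeGeCoach arm only, with usual-care patients and TeGeCoach patients who never had a coach as clusters of size one;
- arm-specific residual variance, fitted by REML with Satterthwaite or Kenward-Roger degrees of freedom.

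In the claims models, use the same coach term, or coach-clustered standard errors with a small-sample correction. State the number of coaches and report the estimated coach ICC.

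**Cost.** Revised wording and one extra data field, a pseudonymised coach identifier. The likely source is the coaching records, since "health coaches use an electronic documentation system to monitor the coaching process", but the documents do not confirm that the field exists or can be transferred. It should be requested before the pseudonymisation keys are deleted, which Data collection and management sets at two years after study completion. Confidence intervals widen only as far as coaches differ: about 2% with 30 coaches and ICC 0.01, and 23% with 10 coaches and ICC 0.05 (the standard error ratios above). If the coach variance is estimated at zero, the result is almost the planned one.
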